### 3.2.2. Rationale for Dose Selection

# **Preclinical**:

Blocking potency of the cocktail of anti-Fel d 1 mAbs was characterized in a preclinical basophil activity test using fresh basophils from cat allergic patients. The utilization of both antibodies (REGN1908-1909) was more effective than either REGN1908 or REGN1909 alone, in the majority of patients in blocking Fel d 1 binding to polyclonal human IgE and inhibiting activation of basophils, as measured by flow cytometry by percent inhibition of phosphorylated extracellular signal-regulated kinase (pERK) responses, from cat allergic patients.

# Clinical:

The PK of REGN1908 and REGN1909 has been consistent across all clinical trials, exhibiting linear PK and a terminal half-life of approximately 31.0±5.9 days and 22.4±3.8 days for REGN1908 and REGN1909, respectively. In a phase 1b study (R1908-1909-ALG-1325) designed to reduce nasal symptoms after a nasal allergen challenge and a phase 2 study (R1908-1909-ALG-1703) that evaluated efficacy of preventing asthma in an EEU, a dose of 600 mg (300 mg/mAb) was well tolerated and maintained efficacy for up to 12 weeks, suggesting that this dose will be safe and efficacious in a phase 3 field study, including after repeat administration. PK data from previous clinical trials in cat allergic humans were used to estimate PK parameters and then simulate repeat SC doses for 300 mg/mAb every 3 months. Maximum (Cmax) and trough (Ctrough) total antibody concentrations in serum are within approximately 10% of single dose Cmax and Ctrough values, indicating that accumulation is expected to be minimal, while also maintaining a Ctrough concentration that is associated with efficacy.

# 3.3. Risk-Benefit

REGN1908 and REGN1909 are human mAbs of the IgG4 isotype that bind different epitopes on Fel d 1 simultaneously, non-competitively, and with high affinity. REGN1908 and REGN1909 are being developed as an antibody cocktail (designated as REGN1908-1909). REGN1908-1909 blocks Fel d 1 from binding and crosslinking receptor bound IgE on the surface of allergic effector cells, thus preventing initiation of the cat allergic response. The clinical proof-of-mechanism study (R1908-1909-ALG-1325) examined the potential of REGN1908-1909 to block acute allergic symptoms triggered by nasal provocation with cat extract in cat allergic patients. The majority of patients receiving REGN1908-1909 experienced symptom amelioration, with at least 50% of patients achieving 60% improvement in TNSS at every time point assessed during nasal allergen challenges up to 12 weeks post-treatment (day 85, last time point assessed) with efficacy demonstrated as early as the first time point evaluated (day 8). This suggests that a majority of cat allergic patients who were treated with REGN1908-1909 may derive benefit by experiencing reduced rhinitis symptoms upon challenge with cat allergen. Additionally, in a proof-of-concept study (R1908-1909-ALG-1703) in cat allergic patients with GINA 1 asthma, REGN1908-1909 increased the time to EAR in the majority of patients and increased the cumulative cat allergen tolerated during cat allergen EEU challenge by 3 fold. These effects were first noted on day 8 (initial time point evaluated post study drug administration) and persisted up to 12 weeks post-treatment, suggesting a potential benefit in cat allergic individuals with mild asthma. Taken together, these results support that a single dose of the REGN1908-1909 cocktail demonstrated a rapid and clinically meaningful effect in reducing the allergic airway response in cat allergic

patients. The treatment may offer a rapid and potentially effective approach for the treatment of cat allergy in patients where there is ongoing exposure to cat allergen or cats cannot be avoided.

REGN1908-1909 has been used to treat 83 subjects in 3 completed clinical studies with no significant clinical safety findings observed to date, including no deaths, and no cases of systemic hypersensitivity, or anaphylaxis. No important identified risks have been established. The important potential risks with REGN1908-1909 (based on preclinical evaluation, mechanism of action targeting an exogeneous antigen, and risks associated with mAbs in general) include systemic hypersensitivity reactions and immunogenicity. REGN1908-1909 has been generally well tolerated and risks have been adequately managed.

To date, no significant safety information with regard to the important potential risks of systemic hypersensitivity reactions and immunogenicity has been reported. Currently, the available safety data along with the risk minimization and monitoring activities support the continued development of REGN1908-1909.

As with most other protein therapeutics that are administered SC, injection site reactions may occur and may be treated symptomatically. Among the 3 completed studies, injection site reactions were reported in 6 patients that received REGN1908-1909, compared to 2 patients in the placebo groups, and all were mild in severity. Allergy/hypersensitivity reactions may develop; the most concerning are those that may develop immediately or within a few hours of administration of REGN1908-1909. Because REGN1908-1909 is composed of antibodies whose sequence is fully human, the risk of these immediate reactions is considered to be extremely low. Emergency equipment and medication for the treatment of these potential adverse effects (including but not limited to antihistamines, corticosteroids, acetaminophen, and/or epinephrine) are available for immediate use in this study. Considering the safety data and the exogenous nature of the target antigen, the risk of other adverse reactions is considered to be low. A risk-benefit statement with respect to the overall development program is provided in the Investigator's Brochure.

An Independent Data Monitoring Committee (IDMC) will be involved in the review of unblinded data in an ongoing manner (refer to Section 6.3.1).

Recognizing that the "Coronavirus Disease 2019" (COVID-19) pandemic will have an impact on the conduct of clinical trials, the Sponsor does not intend to screen any patients in this study until the impact of the COVID-19 pandemic is deemed manageable and no longer interfering with the conduct of trials at individual sites, and patients can safely participate in this study. Until then, the Sponsor plans to obtain approvals from Health Authorities/Ethics Committees (ECs) to enable initiation of study sites for this study, as allowed by local laws and regulations.

#### 4. ENDPOINTS

# 4.1. Primary Endpoint

The primary endpoint is the daily CSMS, averaged over the last 12 weeks of the treatment period (weeks 48 to 60), in patients who receive REGN1908-1909 versus placebo.

Note: CSMS is defined as the daily combined allergic rhinitis and conjunctivitis TSS (calculated as the sum of TNSS and TOSS) plus daily medication score (DMS).

# 4.2. Secondary Endpoints

The key secondary endpoints, specified without order, are:

- Daily TNSS, averaged over the last 12 weeks of treatment period (weeks 48 to 60), in patients who receive REGN1908-1909 versus placebo
- Percent change from pre-treatment baseline in average CSMS, over the last 12 weeks of the treatment period (weeks 48 to 60), in patients who receive REGN1908-1909 versus placebo
- Percent change from pre-treatment baseline in average TNSS, over the last 12 weeks of the treatment period (weeks 48 to 60), in patients who receive REGN1908-1909 versus placebo
- Daily TSS, averaged over the last 12 weeks of the treatment period (weeks 48 to 60), in patients who receive REGN1908-1909 versus placebo
- Percent change from pre-treatment baseline in average TSS, over the last 12 weeks of the treatment period (weeks 48 to 60), in patients who receive REGN1908-1909 versus placebo
- Percent change from baseline to the end of treatment (week 60) in cat SPT mean wheal diameter in patients who receive REGN1908-1909 versus

# Other secondary endpoints, specified without order, are:

- Daily CSMS, averaged over the initial 12 weeks of the treatment period (weeks 0 to 12), in patients who receive REGN1908-1909 versus placebo
- Daily TNSS, averaged over the initial 12 weeks of treatment period (weeks 0 to 12), in patients who receive REGN1908-1909 versus placebo
- Percent change from pre-treatment baseline in average CSMS, over the initial 12 weeks of the treatment period (weeks 0 to 12), in patients who receive REGN1908-1909 versus placebo
- Percent change from pre-treatment baseline in average TNSS, over the initial 12 weeks of the treatment period (weeks 0 to 12), in patients who receive REGN1908-1909 versus placebo
- Percent change from pre-treatment baseline in average TSS, over the initial 12 weeks
  of the treatment period (weeks 0 to 12), in patients who receive REGN1908-1909
  versus placebo

- Daily TSS score, averaged over the initial 12 weeks of the treatment period (weeks 0 to 12), in patients who receive REGN1908-1909 versus placebo
- Percent change from pre-treatment baseline in average TOSS, over the initial 12 weeks
  of the treatment period (weeks 0 to 12), in patients who receive REGN1908-1909
  versus placebo
- Daily TOSS, averaged over the last 12 weeks of the treatment period (weeks 48 to 60), in patients who receive REGN1908-1909 versus placebo
- Percent change from pre-treatment baseline in average TOSS, over the last 12 weeks of the treatment period (weeks 48 to 60), in patients who receive REGN1908-1909 versus placebo.
- Percent change from baseline to week 12 in FEV1 in patients with asthma who receive REGN1908-1909 versus placebo
- Percent change from baseline to week 60 in FEV1 in patients with asthma who receive REGN1908-1909 versus placebo
- Percent change from baseline to week 12 in cat skin prick test (SPT) mean wheal diameter in patients who receive REGN1908-1909 versus placebo
- Change from baseline to week 12 in FEV1 in patients with asthma who receive REGN1908-1909 versus placebo
- Change from baseline to week 60 in FEV1 in patients with asthma who receive REGN1908-1909 versus placebo
- Change from baseline to week 60 in RQLQ(S)+12 in patients who receive REGN1908-1909 versus placebo
- DMS, averaged over the initial 12 weeks of the treatment period (weeks 0 to 12), in patients who receive REGN1908-1909 versus placebo
- DMS, averaged over the last 12 weeks of the treatment period (weeks 48 to 60), in patients who receive REGN1908-1909 versus placebo
- Percent change from pre-treatment baseline in average DMS, averaged over the last 12
  weeks of the treatment period (weeks 48 to 60), in patients who receive REGN19081909 versus placebo
- Percent change from baseline to end of study (week 72) in cat SPT mean wheal diameter in patients who receive REGN1908-1909 versus placebo
- Asthma daily symptom (ADS) score, averaged over the initial 12 weeks of the treatment period (weeks 0 to 12), using Asthma Daytime Symptom Diary (ADSD) and the Asthma Nighttime Symptom Diary (ANSD), in patients with asthma who receive REGN1908-1909 versus placebo
- Asthma daily symptom (ADS) score, averaged over the last 12 weeks of the treatment period (weeks 48 to 60), using Asthma Daytime Symptom Diary (ADSD) and the Asthma Nighttime Symptom Diary (ANSD), in patients with asthma who receive REGN1908-1909 versus placebo

- Daily TOSS, averaged over the initial 12 weeks of the treatment period (weeks 0 to 12), in patients who receive REGN1908-1909 versus placebo
- Change from baseline to week 60 in ACQ-5 in patients with asthma who receive REGN1908-1909 versus placebo
- Daily number of nighttime awakenings, averaged over the initial 12 weeks of the treatment period (weeks 0 to 12), in patients with asthma who receive REGN1908-1909 versus placebo
- Daily number of nighttime awakenings, averaged over the last 12 weeks of the treatment period (weeks 48 to 60), in patients with asthma who receive REGN1908-1909 versus placebo
- Incidence of treatment-emergent adverse events (TEAEs), AESIs, and serious TEAEs throughout the study (weeks 0 to 72)
- Total REGN1908 and REGN1909 concentration in serum over the study duration (weeks 0 to 72)
- Incidence of treatment-emergent anti-drug antibodies (ADAs) to REGN1908 and REGN1909 throughout the study (weeks 0 to 72)

# 4.3. Exploratory Endpoints

The exploratory endpoints are:

- The number of "well days" in those who received REGN1908-1909 versus placebo, over the initial 12 weeks (weeks 0 to 12) of the treatment period; "well days" are defined as days when rescue medication is not utilized and the TSS is <2/18
- The number of "well days" in those who received REGN1908-1909 versus placebo, over the last 12 weeks of the treatment period (weeks 48 to 60); "well days" are defined as days when rescue medication is not utilized and the TSS is <2/18
- Percent change from pre-treatment baseline in average ADS score, over the initial 12 weeks of the treatment period (weeks 0 to 12), using ADSD and the ANSD in patients with asthma who receive REGN1908-1909 versus placebo
- Percent change from pre-treatment baseline in average frequency of asthma rescue medication use, over the initial 12 weeks of the treatment period (weeks 0 to 12), in patients with asthma who receive REGN1908-1909 versus placebo
- Percent change from pre-treatment baseline in average frequency of nighttime awakenings, over the initial 12 weeks of the treatment period (weeks 0 to 12), in patients with asthma who receive REGN1908-1909 versus placebo
- Percent change from pre-treatment baseline in average DMS, over the initial 12 weeks of the treatment period (weeks 0 to 12), in patients who receive REGN1908-1909 versus placebo
- Change from baseline to week 12 in RQLQ(S)+12 in patients who receive REGN1908-1909 versus placebo

- Change from baseline to week 12 in Asthma Control Questionnaire 5 Question Version (ACQ-5) in patients with asthma who receive REGN1908-1909 versus placebo
- Daily frequency of asthma rescue medication use, averaged over the initial 12 weeks of the treatment period (weeks 0 to 12), in patients with asthma who receive REGN1908-1909 versus placebo
- Daily frequency of asthma rescue medication use, averaged over the last 12 weeks of the treatment period (weeks 48 to 60), in patients with asthma who receive REGN1908-1909 versus placebo

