# 2.3. Exploratory Objectives

• To evaluate "well days"

Note: "Well days" are defined as days when the TSS is  $\leq 2$  without the use of anti-allergy rescue medications.

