4.5.4. Exploratory Variables

The exploratory endpoints are:

- The number of “well days” over the initial 12 weeks (weeks 0 to 12) of the treatment period; “well days” are defined as days when rescue medication is not utilized and the TSS is $\leq 2/18$
- The number of “well days” over the last 12 weeks of the treatment period (weeks 48 to 60); “well days” are defined as days when rescue medication is not utilized and the TSS is $\leq 2/18$
- Percent change from pre-treatment baseline in average ADSS, over the initial 12 weeks of the treatment period (weeks 0 to 12), using ADSD and the ANSD
- Percent change from pre-treatment baseline in average frequency of asthma rescue medication use, defined as the number of puffs of a short-acting bronchodilator and an inhaled steroid over the past 24 hours, over the initial 12 weeks of the treatment period (weeks 0 to 12), in patients with asthma
- Percent change from pre-treatment baseline in average frequency of nighttime awakenings, over the initial 12 weeks of the treatment period (weeks 0 to 12), in patients with asthma
- Percent change from pre-treatment baseline in average DMS, over the initial 12 weeks of the treatment period (weeks 0 to 12)
- Change from baseline to week 12 in RQLQ(S)+12
- Change from baseline to week 12 in Asthma Control Questionnaire 5 Question Version (ACQ-5) in patients with asthma
- Daily frequency of asthma rescue medication use, averaged over the initial 12 weeks of the treatment period (weeks 0 to 12), in patients with asthma
- Daily frequency of asthma rescue medication use, averaged over the last 12 weeks of the treatment period (weeks 48 to 60), in patients with asthma

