2. Must have a least 8 unique days of a DMS score >0 within the same 15 consecutive day period as Criteria 1. The 8 unique days do not have to occur on the same days as Criteria 1; however, they must be within the same 15 consecutive days.

If less than 15 days of data are available during the baseline assessment period, the baseline will be the average CSMS over all available days (if duplicate entries of CSMS are available on the same day, the worst score will be used).

Only days with observed data will be included in the calculation of average score. The average CSMS (max score 38/day) will be calculated based on the sum of average daily TNSS (max score 12/day), average daily TOSS (max score 6/day) and average daily medication scores (DMS, max of 20/day) recorded over the last 12 weeks of the treatment period (weeks 48 to 60).

For the MI procedure, missing data (the average CSMS) will be imputed 50 times to generate 50 complete data sets utilizing the SAS procedure PROC MI. Note that any imputation by worst CSMS score as specified in [Table 4](#) will occur prior to MI. The 2 steps below will be followed for MI:

Step 1: The Markov Chain Monte Carlo (MCMC) method will be used to fill in missing values of average CSMS during weeks 0-12 by treatment group so that a monotone missing pattern will be formed.

Step 2: Using the data sets from Step 1, missing values of average CSMS from weeks 48-60 will be imputed using a monotone regression method. The imputation model will include the covariates in the ANCOVA model and the average CSMS from weeks 0-12.

For steps 1 and 2, any score imputed outside the range of CSMS (0-38) will be truncated to the nearest value of CSMS according to the following algorithm:

- If the imputed score > 38, then the final imputed score will be 38.
- If the imputed score < 0, then the final imputed score will be 0.

Sample SAS syntax code for MI:

```
proc mi data=mi1 out=mi3 noint nimate=50 seed=190819;
mcmc impute=monotone;
var BASELINE CSMS012 CSMS4860;
by TRTP;
run;

proc mi data=mi3 out=mi4 nimate=1 seed=190819;
class TRTP STRAT1 STRAT2 STRAT3 CATIGE;
monotone reg;
var TRTP STRAT1 STRAT2 STRAT3 CATIGE BASELINE CSMS012;
by _imputation_;
run;
```

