5.6.5. Analysis of Exploratory Efficacy Variables

For continuous exploratory efficacy variables, e.g., percent change in ADSS, they will be analyzed by using an ANCOVA model similar to the analyses of primary endpoint.

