6.5. Visit Windows

Data collected by daily diary will be summarized by the study treatment period (the initial 12 weeks, or the last 12 weeks). The last (initial) 12 weeks will be defined as below:

Treatment period	Collected days $\geq 84^*$	Collected days < 84
Initial 12 weeks	[date of Visit 3, date of Visit 3 + 84)	[date of Visit 3, date of Visit 6)
Last 12 weeks	[date of Visit 12, date of Visit 12 + 84)	[date of Visit 12, date of Visit 14]

* Collected days = (date of visit 6 – date of visit 3 + 1) for the initial 12 weeks ; Collected days = (date of visit 14 – date of visit 12 + 1) for the last 12 weeks.

Data analyzed by-visit-analysis (efficacy [excluding daily diary data], laboratory data, vital sign) will be summarized by the study scheduled visits described in the study protocol and SAP “Schedule of Events”. The analysis visit windows will be exhaustive so that all available values obtained from unscheduled visits and early termination (ET) visit have the potential to be summarized. No analysis visit windows will be applied for the study scheduled visits.

The analysis visit windows are created per study Schedule of Events (SOE) table for each parameter and will be applied if the data from study scheduled visits are unavailable. The following general rules will be applied to unscheduled visit and/or ET visit mapping for each parameter.

1. If ET due to an AE or lack of efficacy, the ET data for efficacy will not be mapped and the next scheduled visit data will be imputed using the worst score of all the observations in corresponding treatment group; if ET due to random reason, the ET data for efficacy will be mapped using rule 2 below. (Safety data will be mapped in either scenario.)
2. If ET visit falls in an analysis window which already has non-missing observed value of this parameter from the scheduled visit, ET will be mapped to the next scheduled visit.
3. If both ET visit and unscheduled visit of the same parameter are available in the same analysis visit window, only ET visit will be mapped.

4. If multiple unscheduled visits of the same parameter are available in the same analysis visit window, the unscheduled visits will be mapped using the following rules:
 - a. The closest unscheduled visit from the target day will be selected.
 - b. If multiple unscheduled visits exist on the same day, the first unscheduled visit will be used.

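### Well days is an unscaled count, so missed diary nights and short visit windows lower it just as unwell days would; Protocol 4.3 also uses a different symptom cut-off from Protocol 2.3 and the SAP.

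*Protocol*

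**What the plan says.** Protocol 4.3 lists well days for weeks 0 to 12 and weeks 48 to 60, the latter as "The number of 'well days' in those who received REGN1908-1909 versus placebo, over the last 12 weeks of the treatment period". SAP 4.5.4 lists the same two counts. Neither document states a denominator, a minimum number of diary days or a scaling rule.

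The cut-off differs by place. Protocol 4.3 counts "days when rescue medication is not utilized and the TSS is <2/18", for both periods. Protocol 2.3 sets the limit at 2 or less, as do SAP 1.2.3 and SAP 4.5.4: "days when rescue medication is not utilized and the TSS is $\leq 2/18". SAP 1.2.4 lists the departures from the protocol's statistical section and does not mention this one.

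For averaged scores, SAP 5.6.1 says: "Only days with observed data will be included in the calculation of average score". For continuous exploratory variables, SAP 5.6.5 says "they will be analyzed by using an ANCOVA model similar to the analyses of primary endpoint" and does not name well days. SAP 6.5 sets the full diary window for the last period as "date of Visit 12, date of Visit 12 + 84" and ends it at Visit 14 when fewer than 84 days are collected.

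**The concern.** The symptom and medication scores, the asthma daily symptom score, nighttime awakenings and asthma rescue use are all averaged over the period. Under the observed-days rule, a missed night leaves both numerator and denominator of an averaged score. Well days has no denominator. A night without an entry cannot be shown to be well, so it lowers the count as an unwell night would. The count therefore mixes symptom control with diary completion, time in the window and visit dates.

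Well days is the only stated exploratory objective. If the cut-off, the denominator and the handling of patients without data are left open, they could be settled after unblinding. The result could then differ with choices unrelated to symptom control.

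**Working it through.** The plan gives no planning figure for well days, so there is none to reproduce. The check covers the countable window, its effect on a count, and the wording.

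**Inputs.** Protocol Table 3: Visit 3 on day 1, Visit 6 on day 85 ±14, Visit 12 on day 337 ±14, Visit 14 on day 421 ±7. SAP 6.5: collected days = last visit date − first visit date + 1. If this is at least 84, the window is 84 days. If it is less, the window runs from Visit 3 up to but excluding Visit 6, or from Visit 12 through Visit 14.

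**Countable days**

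- Weeks 48 to 60, on target: 421 − 337 + 1 = 85, so 84 days count.
- Weeks 48 to 60, shortest: Visit 12 on day 351 and Visit 14 on day 414 give 414 − 351 + 1 = 64 days.
- Weeks 0 to 12, on target: 85 − 1 + 1 = 85, so 84 days count.
- Weeks 0 to 12, shortest: Visit 6 on day 71 gives 71 − 1 = 70 days.

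Largest shortfall: 1 − 64/84 = 24% and 1 − 70/84 = 17%.

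To show how typical that is, assume that every pair of permitted Visit 12 and Visit 14 dates is equally likely: 29 × 15 = 435 pairs. Of these, 195 (45%) give fewer than 84 days. The mean is 80.5 days, and only one pair gives 64.

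**Effect on the count.** Expected count = daily well-day rate × countable recorded days. The rates are assumptions; the documents give none.

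| Assumed rate | 84 days | 70 days | 64 days | 84 days, 20% of nights missed |
|---|---|---|---|---|
| 10% | 8.4 | 7.0 | 6.4 | 6.7 |
| 30% | 25.2 | 21.0 | 19.2 | 20.2 |
| 50% | 42.0 | 35.0 | 32.0 | 33.6 |

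As a proportion of recorded days, each row returns its own rate, provided nights are missing at random.

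**Patients with no data in the window.** Suppose, as one possible handling, that they score 0 and that the true rate is 30% in both arms. False difference = 84 × 0.30 × (placebo dropout − active dropout).

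- 20% in each arm (the plan's overall dropout assumption): 0 days.
- 25% vs 15%: 84 × 0.30 × 0.10 = 2.5 days.
- 30% vs 10%: 84 × 0.30 × 0.20 = 5.0 days.

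Equal dropout dilutes instead: a true gap of 10 percentage points (8.4 days) becomes 8.4 × 0.80 = 6.7 days. The unequal splits are assumptions.

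**Would the primary endpoint's rules close the gap?** If SAP 5.6.5 is read to import SAP Table 4, worst-score and multiple imputation reach only patients with no available CSMS in the window. Scattered missed nights and dropout part-way through stay uncovered. Table 4 also sets diary data to missing during travel of 42 or more consecutive days, which in a count could remove at least 42/84 = 50% of a full window.

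**Cut-off.** TSS sums six items graded 0 to 3, so the daily value is a whole number. Protocol 4.3 admits 0 and 1; Protocol 2.3 and the SAP admit 0, 1 and 2. The disputed days are rescue-free days with TSS exactly 2.

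**The case against.** The strongest reply is that the documents never adopt a harmful rule. A reader might infer that missed nights and dropouts are scored as not well. No section says so: for intermittent nights it is the arithmetic result of a count with no other rule, and for patients with no data the handling is unspecified, or imputed if SAP 5.6.5 brings in Table 4. This stands.

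A reader might also take 24% as a typical distortion, or as a bias. It is one corner of the visit windows. The schedule is the same in both arms and site staff and patients are blinded, so visit timing should mainly add noise. This stands too.

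On the cut-off, the SAP governs the analysis and uses 2 or less throughout, so the error may be confined to one protocol section. A symbol lost in reading the PDF cannot be excluded. It is also tempting to convert the planning TSS mean of 4.2 and SD of 3.0 into a share of disputed days. Those figures describe scores averaged over the period, not single days, so they cannot support such a conversion.

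Finally, the endpoint is outside the 13-step hierarchy in SAP 5.6.3 and drives no sample-size, futility or success decision. That limits the weight of the point. It does not remove the missing denominator or missing-data rule.

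**Conclusion.** The point holds as a low-priority correction. Well days is an unscaled count in both documents. At the same daily rate it can fall by up to 24% (weeks 48 to 60) or 17% (weeks 0 to 12) through visit timing alone, with no loss when visits are on target. Missed nights and dropout within the window lower it further.

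Equal missingness across arms adds noise or dilutes a difference. A false difference needs unequal missingness, which the documents neither state nor suggest. The 2.5-day and 5.0-day figures also depend on zero scoring and a 30% rate.

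The cut-off conflict lies within the protocol, and between Protocol 4.3 and the SAP, subject to a check of the source page. Its effect on the number of well days cannot be sized from the documents.

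**What to change.** 1. In Protocol 4.3 and SAP 4.5.4, define the endpoint as the proportion of diary days in the window with complete TSS and rescue-medication entries that are well days, multiplied by 84 if a day count is wanted for display. A count model with log observed days as offset is an alternative. Name the chosen analysis in SAP 5.6.5.
2. Set a minimum number of diary days before unblinding; otherwise one recorded good night gives 100%. The documents offer no basis for a particular value.
3. Handle patients below the minimum, or with no data, by the primary endpoint's rules: worst value in the arm after discontinuation for adverse events or lack of efficacy, multiple imputation otherwise. State that worst here means the lowest proportion.
4. Check the source page of Protocol 4.3 and align its cut-off to 2 or less, as in Protocol 2.3 and the SAP.

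The cost is wording, one derived variable and its programming, with no new data or procedures. The proportion relies on a patient's missed nights being missing at random, as the average used for the primary endpoint already does.
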